10.8. Appendix 8: Country-specific Requirements

10.8.1. France Contrat Unique

This country specific appendix captures operational items not included in the mandatory contract format for France (i.e. French “Contrat Unique”), which Pfizer includes in standard contract language for other countries.

1. GCP Training

Before enrolling any participants, the investigator and any subinvestigators will complete the Pfizer-provided Good Clinical Practice training course (“Pfizer GCP Training”) or training deemed equivalent by Pfizer. Any investigators who later join the study will do the same before performing study-related duties. For studies of applicable duration, the investigator and subinvestigators will complete Pfizer GCP Training or equivalent every 3 years during the term of the study, or more often if there are significant changes to the ICH GCP guidelines or course materials.

2. Study Intervention

No participants or third-party payers will be charged for study intervention.

3. Record Retention

If the investigator becomes unable for any reason to continue to retain study records for the required period (e.g., retirement, relocation), Pfizer should be prospectively notified. The study records must be transferred to a designee acceptable to Pfizer, such as another investigator, another institution, or to an independent third party arranged by Pfizer. Investigator records must be kept for a minimum of 15 years after completion or discontinuation of the study or for longer if required by applicable local regulations. The investigator must obtain Pfizer’s written permission before disposing of any records, even if the retention requirements have been met.

4. SUSARs

Pursuant to a sponsor’s safety reporting obligations under 21 CFR 312.32(c)(1), Pfizer will report to the investigator all Serious Unexpected Suspected Adverse Reactions (“SUSARs”). Investigator will receive and review SUSAR reports and report SUSARs to the responsible IRB/IEC according to institution’s guidelines. Institution will retain SUSAR reports consistent with Section [10.1.7](#) of the Protocol.

5. Collection of Ethnic Origin Information

Information regarding ethnic origin will be collected in this study in compliance with the French Data Protection Authority (CNIL): Deliberation no. 2016-262 of 21 July 2016 amending the reference methodology for the processing of the personal data conducted in connection with biomedical research (MR-001), § 2.2.3 Nature of the data.

Individuals participating in this study will consent that this information can be collected in the study before they enter the study.

The electronic Case Report Form (eCRF) will be used as the source file for ethnic origin in France. This information will not be recorded in the participant's medical records.

[figure not shown]
10.8.2. Japan-specific Regulatory Requirements

10.8.2.1. Definitions of Serious Adverse Event, Serious Adverse Event Caused by Medical Device, and Unanticipated Serious Adverse Event Caused by Medical Device

Definition of serious adverse event caused by medical device

A serious adverse event caused by medical device is defined as an adverse event caused by a medical device which led to an outcome characteristic to serious adverse events, or a device-related incident whose recurrence might lead to death or serious deterioration in health.

10.9. Appendix 9: Decision Algorithm for Disease Assessment

Abbreviations: CIS = carcinoma in situ

The above diagram illustrates how cystoscopy, urine cytology, biopsy and imaging should be integrated to assess achievement of CR for participants with CIS at baseline, recurrence of high-grade disease, persistence of CIS or progression of disease. Participants enrolled in Cohort A with CIS with persistent disease and participants with recurrence of high-grade Ta disease following first induction period are eligible for a re-induction period of up to 6 additional weekly doses of BCG treatments (see study Schema for Cohort A). Below, definitions are provided for no evidence of disease, CR, recurrence of high-grade disease, persistence of CIS, and progression of disease.

Cytology results are defined as the following:

1. Positive - if indicative or suggestive of malignant cells:
 - High-grade urothelial carcinoma
 - Suspicious for high-grade urothelial carcinoma
2. Negative if NOT indicative or suggestive of malignant cells:
 - Negative for high-grade urothelial carcinoma cells
 - Presence of low-grade urothelial carcinoma cells
 - Atypical urothelial cell not abnormal enough to be considered as cancerous

3. Indeterminate: unsatisfactory sample.

In Cohort B1, when cystoscopy is negative and cytology is positive at a given disease assessment timepoint, biopsies must be collected from the bladder dome, trigone, right lateral wall, left lateral wall, anterior and posterior wall, and prostatic urethra for male participants.

For participants in Cohort B1, decision to continue treatment following disease assessment will be made by the investigator as described in the diagram above with BICR review of disease assessment (including tumor tissue samples, cytology, cystoscopy and imaging) occurring in an expedited manner. For participants in Cohort B1 continuation of treatment for 1 additional cycle while waiting for confirmation of recurrence of high-grade Ta, T1 or CIS disease by the BICR will be allowed at the discretion of the investigator. If the 12 week disease assessment is “Not Evaluable” per the BICR, the assessment with a non-evaluable result should be repeated as soon as possible.

In case of discordant results at a given disease assessment timepoint with negative cytology as assessed by the investigator and positive cytology as assessed by the BICR, the following assessments should be performed as soon as possible:

- Cystoscopy with collection of random biopsies from bladder (dome, trigone, right and left lateral wall, and anterior and posterior wall) and prostatic urethra in male participants OR collection of suspicious lesions, if present;
- Cytology;
- Imaging

No Evidence of Disease only applies to participants without CIS at baseline (Cohort A and Cohort B2) and is defined as disease that was completely resected prior to randomization (Cohort A)/initiation of study intervention (Cohort B2) and does not meet the criteria of progression of disease, recurrence of high-grade disease, or recurrence of low-grade disease while on study. The date of imaging, biopsy, cystoscopy, or cytology (whichever result of the available assessments is earliest) that supports no evidence of disease will be used as the date of no evidence of disease.

Complete Response, in participants with CIS at baseline, is defined as histologic disappearance of malignancy on bladder biopsy with negative cytology and cystoscopy or negative cytology and positive cystoscopy with biopsy-proven low-grade Ta lesion or non-malignant tissue. The date of biopsy, cystoscopy, or cytology (whichever is earliest) will be used as the date of Complete Response. See section 8.1.1.1 for guidance regarding timing of these biopsies.

Persistence of CIS, in participants with CIS at baseline in Cohort A, is defined as persistence of CIS after induction or re-induction (if re-induction is administered). For participants in Cohort B1, persistence of CIS is defined as persistence of CIS at the 12 week or 24 week disease assessment. This will require a cystoscopy or cytology positive result with biopsy positive for CIS. The date of positive biopsy, cystoscopy, or cytology (whichever positive result is earliest) will be used as the date of persistence of CIS.

Recurrence of high-grade disease is defined as re-appearance of high-grade disease (high-grade Ta, T1 or CIS) after randomization/initiation of study intervention or re-appearance of high-grade disease after CR for participants with CIS at baseline or re-appearance of high-grade disease before CR for participants with CIS and concurrent papillary disease at baseline in Cohort A or B1. This will require a cystoscopy or cytology positive result, with biopsy positive for T1, high-grade Ta and/or CIS. The date of positive biopsy, cystoscopy, or cytology (whichever positive result is earliest) will be used as the date of recurrence of high-grade disease. In Cohort B1, if the investigator determines that high-grade disease is present, the participant may continue on study for 1 additional cycle, until BICR review confirms diagnosis of high-grade disease. At that time, if high-grade disease recurrence is confirmed by the BICR, the participant must discontinue study treatment.

Recurrence of low-grade disease is defined as re-appearance of low-grade disease (low-grade Ta) after randomization (Cohort A)/initiation of study intervention (Cohort B). This will require a cystoscopy or cytology positive result, with biopsy positive for low-grade Ta. The date of positive biopsy, cystoscopy or cytology (whichever positive result is earliest) will be used as the date of recurrence of low-grade disease.

Progression of disease is defined as any of the following:

- Lamina propria invasion (eg, increase from Ta to T1 or CIS to T1)
- Muscle invasive disease (stage \geq T2)
- Lymph node positive disease (N $+$)
- Metastatic disease (M1)
- Appearance of high-grade Ta or T1 in participants with CIS only at baseline (Cohort A and Cohort B1) before achieving a CR.

This will require a cystoscopy or cytology positive result with imaging positive and/or biopsy positive for disease progression as described above. The date of positive biopsy, imaging for new lesion, positive cystoscopy, or positive cytology (whichever positive result is earliest) will be used as the date of progression.

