Event - After at most one missing or inadequate post-baseline disease assessment, OR - \leq 24 weeks after the date of randomization	Date of event	Event
Event - After 2 or more missing or inadequate post-baseline disease assessments	Date of last adequate disease assessment [b] documenting no event	Censored
No event	Date of last adequate disease assessment [b] documenting no event	Censored

[a] However, if the participant dies \leq 24 weeks after the date of randomization the death is an event with date on death date

[b] An adequate post-baseline disease assessment is defined as an assessment with progression of disease (all participants), recurrence of high-grade disease (all participants), recurrence of low-grade disease (all participants), CR (participants with CIS at randomization), persistence of CIS disease (participants with CIS at randomization), or no evidence of disease (participants with papillary disease and no CIS at randomization).

Key Secondary Estimand (OS): treatment effect, estimated based on data from all randomized participants, of each experimental arm (Arm A and Arm B) on OS compared to Arm C regardless of tolerability, duration of study treatment, initiation of subsequent anti-cancer therapy or participant's request to discontinue study procedures.

- Variable: OS.

- Censoring: data for participants not known to have died are censored at the time of last contact.
- Population-level summary measure: hazard ratio for OS, including all randomized participants.

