1.1 Synopsis 1.2 Study Schema 1.3 Schedule of Activities 2.1 Study Rationale 2.1.2 Study Rationale for the BCG-Unresponsive Cohort (Cohorts B1 and B2) 2.2.1 Clinical Background 2.3 Benefit/Risk Assessment 3.2 Objectives, Estimands and Endpoints for Cohorts B1 and B2 4.1.2 Overall Design Cohorts B1 and B2	Language was added to support the dosing modification to Cohort B2. Updated language provides rationale for the updated design, and updates to objectives, endpoints, and study procedures for Cohort B2.	Update was included to support updated Cohort B2 dosing regimen.
---	--	--

4.3.1 Justification for Dose of PF-06801591 6.1 Study Intervention Administered 7.1 Discontinuation of Study Intervention 8.4 Treatment of Overdose		
1.3 Schedule of Activities	Frequency of urinalysis was updated for Cohorts B1 and B2.	Updated to more clinically appropriate time points.
5. Study Population	Sentence was added to describe Sponsor eligibility approval process.	Process update added for clarification to sites.
5.1 Inclusion Criteria	Allowance for prior treatment with Verity strain of BCG was added.	Verity strain is the same strain as the Imuron-vac strain, but with a different brand name. Allowance added for clarity.
8.5 Pharmacokinetics 9.4.3.2 Pharmacokinetics	Post-dose PK samples were added for participants in Cohort B2.	Sampling time point was added to support PK analysis of Cohort B2 dosing regimen.
10.2 Clinical Laboratory Tests Table 6	Creatine kinase testing was added to the chemistry panel for Cohorts B1 and B2.	Test added to support collection of additional safety data for Sasanlimab.
10.9 Decision Algorithm for Disease Assessment	Definition of “No Evidence of Disease” was added, as this previously appeared only in the CRF completion guidelines but not in the protocol.	Clarification to sites.
1.1 Synopsis 3.2 Objectives, Estimands and Endpoints for Cohorts B1 and B2	Clarification of censoring strategy and primary estimand text for Cohorts B1 and B2.	Editorial update.

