### **5.2.11. Adequate post-baseline disease assessment**

An adequate post-baseline disease assessment is defined as an assessment recorded with progression of disease (all participants), recurrence of high-grade disease (all participants), recurrence of low-grade disease (participants without CIS at randomization (Cohort A/Cohort B2), CR (participants with CIS at randomization (Cohort A)/baseline (Cohort B1)), persistence of CIS disease (participants with CIS at randomization (Cohort A)/baseline (Cohort B1), or no evidence of disease (participants without CIS at randomization (Cohort A)/baseline (Cohort B2)) (Section 5.2.12). Time points where the response is not evaluable (NE) or no assessment was performed will not be used for determining the censoring date.

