### **5.2.12. Disease Assessments**

Disease will be assessed based on reported results from cytology, cystoscopy, biopsy, and imaging scans at different evaluation time points from the ‘start date’ until the first documentation of progression of disease, recurrence of high-grade disease, or persistence of CIS disease according to the following rules.

**Complete Response**, in participants with CIS at randomization (Cohort A)/baseline (Cohort B1), is defined as:

- histologic disappearance of malignancy on bladder biopsy with negative cytology and cystoscopy; or
- negative cytology and positive cystoscopy with biopsy-proven low-grade Ta lesion or non-malignant tissue.

The date of biopsy, cystoscopy, or cytology (whichever is earliest) will be used as the date of CR.

**Persistence of CIS**, in participants with CIS at randomization in Cohort A, is defined as persistence of CIS after induction or re-induction (if re-induction is administered). For participants in Cohort B1, persistence of CIS is defined as persistence of CIS at the 12-week disease assessment. This will require a cystoscopy or cytology positive result with biopsy positive for CIS. The date of positive biopsy, cystoscopy, or cytology (whichever positive result is earliest) will be used as the date of persistence of CIS.

**Recurrence of high-grade disease** is defined as re-appearance of high-grade disease (high-grade Ta, T1 or CIS) after ‘start date’ for the following 1) participants without CIS at baseline, 2) after CR for participants with CIS at baseline, or 3) before CR for participants with CIS and concurrent papillary disease at baseline in Cohort A or B1. This will require a cystoscopy or cytology positive result, with biopsy positive for T1, high-grade Ta and/or

CIS. The date of positive biopsy, cystoscopy, or cytology (whichever positive result is earliest) will be used as the date of recurrence of high-grade disease. If recurrence of high-grade disease occurs at the time of progression, progression should be the event. For participants with CIS at randomization, appearance of high-grade disease after a CR is considered recurrence of high-grade disease, while appearance of high-grade disease before a CR is progression.

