**Table 11. Outcome and Event Dates for the Primary Analysis of EFS-Cohort A**

Scenario	Date of event/censoring	Outcome
No adequate baseline assessment	Date of randomization [a]	Censored [a]
Event - After at most one missing or inadequate post-baseline disease assessment, OR - $\leq 24$ weeks after the date of randomization	Date of event	Event
Event - After 2 or more missing or inadequate post-baseline disease assessments	Date of last adequate disease assessment documenting no event	Censored
No event	Date of last adequate disease assessment documenting no event	Censored

[a] However, if the participant dies  $\leq 24$  weeks after the date of randomization the death is an event with date on death date

The primary efficacy analysis will compare the EFS time based on the investigator assessment between Arm A and Arm C and will be performed using a 1-sided stratified log-rank test as described in [Section 5.1](#). The following analyses will be based on the FAS.

The treatment effect will be estimated using a Cox's Proportional Hazard model stratified by the randomization strata to calculate the hazard ratio along with 95% CIs. Each stratum will define a separate baseline hazard function (using the 'STRATA' statement in SAS PROC PHREG), ie for the i-th stratum the hazard function is expressed as:  $h(i;t) = h(i,0;t) \exp(x\beta)$ ,

where  $h(i,0;t)$  defines the baseline hazard function for the  $i$ -th stratum and  $x$  defines the treatment arm (0=control arm, 1= experimental arm) and  $\beta$  is the unknown regression parameter.

Ties will be handled using the Exact option in SAS (Ties=Exact option in SAS PROC PHREG).

Kaplan-Meier estimates (product-limit estimates) will be presented by treatment arm together with a summary of associated statistics including the median EFS time with 2-sided 95% CIs. In particular, the EFS rate at 6, 12, 18, 24, 30, 36, 42, and 48 months will be estimated with corresponding 2-sided 95% CIs. The CIs for the median will be calculated according to Brookmeyer and Crowley (1982) and the CIs for the survival function estimates at the time points defined above will be derived using the log-log transformation according to Kalbfleisch and Prentice (2002) (conftype=loglog default option in SAS Proc LIFETEST) with back transformation to a CI on the untransformed scale. The estimate of the standard error will be computed using Greenwood's formula. A Kaplan-Meier plot for EFS will be generated.

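### In Cohort A participants without CIS, a clean visit after a resected low-grade recurrence has, as written, no adequate-assessment category, so some later EFS events would be censored from the primary analysis

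*Protocol*

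**What the plan says.** Protocol Table 2 and SAP Table 10 class low-grade recurrence as not an EFS event. Disease assessment for EFS continues until progression, high-grade recurrence or persistence of CIS (SAP Section 6.1.1.1).

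Protocol Table 3, footnote [b], and SAP Section 5.2.11 define an adequate post-baseline assessment by a list. For a participant without CIS the entries are progression, high-grade recurrence, low-grade recurrence, "or no evidence of disease (participants without CIS at randomization". The other two entries, complete response and persistence of CIS, belong to participants with CIS.

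NED is defined in Protocol Section 10.9 and repeated in SAP Section 5.2.12. It applies only without CIS at baseline and covers disease completely resected before randomization (the start date in the SAP) that "does not meet the criteria of progression of disease, recurrence of high-grade disease, or recurrence of low-grade disease while on study". Its date is that of the earliest available assessment "that supports no evidence of disease will be used as the date of no evidence of disease".

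In Protocol Table 3 and SAP Table 11, an event counts if it follows at most one missing or inadequate assessment, or falls within 24 weeks of randomization. An event "After 2 or more missing or inadequate post-baseline disease assessments" is censored at the last adequate assessment without an event. Event-free participants are censored at that same point.

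**The concern.** The NED definition and the list of adequate assessments do not fit together once a low-grade recurrence has occurred. Two parts of the definition shut out a later clean visit. The low-grade exclusion runs over time on study and is not limited to the current visit. In addition, a tumour resected on study is not disease that was resected before randomization. The visit cannot be coded as low-grade recurrence either, because that needs a positive cystoscopy or cytology with a positive biopsy.

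At stake is the event and censoring status in the primary analysis. True high-grade recurrences, progressions or deaths could be removed, although the estimand counts the earliest of these. Event-free follow-up could be cut back in participants who have been examined and found clear. SAP Section 6.2.2.8 compares low-grade recurrence between arms. If the rates differed, the censoring would differ too; nothing in the documents shows that they do.

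**Working it through.** **Plan's own figure.** Inputs from SAP Section 5.1.1: 174 EFS events for Arm A vs Arm C, HR 0.69, one-sided alpha 0.025. Power = Φ(|ln 0.69| × √(174/4) − 1.96) = Φ(0.371 × 6.595 − 1.96) = Φ(0.487) = 68.7%, as stated. The figure is sound and is not adjusted here, for the reasons under the verdict.

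**Classifying the visit.** Take a participant without CIS, with an earlier low-grade Ta recurrence resected on study and now negative cystoscopy and cytology.

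- Progression or high-grade recurrence: no, nothing is positive.
- Low-grade recurrence: no, it needs positive findings and biopsy.
- Complete response or persistence of CIS: not applicable without CIS.
- NED: not met as written.

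No adequate category remains. The low-grade visit itself is adequate and shows no EFS event, so it becomes the fallback date.

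**Applying the censoring rule.** Visits are every 12 weeks for 2 years, then every 24 weeks, taken here as weeks 12, 24, …, 96, 120, 144, 168. Every other visit is assumed done and adequate.

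| Low-grade recurrence (week) | Clean visits between (weeks) | High-grade event (week) | NED as written | NED per assessment |
|---|---|---|---|---|
| 12 | none | 24 | event, week 24 | event, week 24 |
| 12 | 24 | 36 | event, week 36 | event, week 36 |
| 12 | 24, 36 | 48 | censored, week 12 | event, week 48 |
| 24 | 36, 48 | 60 | censored, week 24 | event, week 60 |
| 96 | 120 | 144 | event, week 144 | event, week 144 |
| 96 | 120, 144 | 168 | censored, week 96 | event, week 168 |

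The two versions differ only when at least two clean visits intervene and the event is later than 24 weeks after randomization. A death in place of the high-grade event follows the same rule.

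**Event-free case.** With low-grade recurrence at week 48 and clean visits through week 144, censoring falls at week 48 as written and at week 144 per assessment: 144 − 48 = 96 weeks of observed follow-up set aside.

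**Planned sensitivity analyses (SAP Section 6.2.2.3).** The analysis that counts all events would restore the censored events. It does not lengthen event-free follow-up, and it also readmits events after visits that really were missed, so it cannot isolate this problem. The imputation for informative censoring covers only loss to follow-up, withdrawal of consent and absence of an adequate post-baseline assessment. Under Table 12, an event-free participant affected here who has not withdrawn or been lost is labelled as ongoing without an event, so the shortened follow-up would not be visible.

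**The case against.** The best answer is that NED is a visit-level status. It carries the date of a supporting assessment, and SAP Section 5.2.12 opens with "Disease will be assessed based on reported results from cytology, cystoscopy, biopsy, and imaging scans at different evaluation time points". The reference to time on study may only contrast with the resection before randomization in the same sentence. A fully literal reading also proves too much: a participant with high-grade recurrence at month 30 would not have been NED at month 3. Finally, SAP Section 5.2.11 bars only non-evaluable or unperformed time points from setting the censoring date, and a clean visit is neither.

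This shows that the visit-level reading is open and probably what was meant. It does not show that either document adopts it. The literal text still excludes the visit, the list of adequate categories is closed, and the two readings give different primary-endpoint status for the same participant.

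A reader might also infer more than the documents support:

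- That everyone with a low-grade recurrence is affected. NED applies only without CIS. Participants with CIS are classified by complete response, which allows a biopsy-proven low-grade Ta lesion.
- That every later event is lost. With no or one clean visit between, or within 24 weeks of randomization, the event counts.
- That sites recorded visits this way. Protocol Section 10.17 (Amendment 3) says the definition was added "as this previously appeared only in the CRF completion guidelines but not in the protocol". Those guidelines are not available here, and how visits after a low-grade recurrence were coded is not shown.

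**Conclusion.** The point holds for Cohort A participants without CIS at randomization. As written, the definition of NED leaves a clean visit after a resected low-grade recurrence without an adequate category. The primary EFS rule would then censor at the low-grade visit any event that comes more than 24 weeks after randomization with two or more such visits before it. Event-free participants would be censored there as well. The all-events sensitivity analysis reduces the risk to interpretation but is not the primary test.

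The size cannot be determined. It depends on the low-grade recurrence rate, the high-grade hazard afterwards and how the visits were coded, and the documents give none of these. It may be nil if visits were classified one at a time. It is tempting to take an assumed share off the 174 events and quote lower power, but the documents do not support that. The 174 is projected from blinded observed EFS accrual (Protocol Section 9.2.1, SAP Section 2). If those events were counted under the same rule, any loss is already in the figure.

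**What to change.** In Protocol Section 10.9 and SAP Section 5.2.12, define NED at each assessment: no disease meeting the criteria for progression, high-grade recurrence or low-grade recurrence at that assessment, including after resection of an earlier low-grade recurrence. In SAP Section 5.2.11, state that such a visit is an adequate assessment documenting no event.

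Before the database snapshot for the primary analysis, derive the status of these visits from the cystoscopy, cytology and biopsy results already collected. SAP Section 7.1 says summaries by arm are unavailable to the study team until that snapshot, so the rule can be fixed without sight of its effect on the comparison.

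The cost is a short wording change in each document and a small re-derivation of visit status. No new data are needed and participant care does not change.
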